16.4. VITAL SIGNS

The following Vital Signs measurements will be reported for this study:

- Supine Systolic Blood Pressure (mmHg)
- Supine Diastolic Blood Pressure (mmHg)
- Supine Pulse Rate (bpm)

The following summaries will be provided for vital signs data:

- Actual assessments at screening, baseline (pre-dose of single dose) and each post-dose timepoint (1, 2, 4, 8, 12 and 24 hours [Day 2])
- Change from Baseline at each post-dose timepoint assessment
- Incidence of markedly abnormal values based on the criteria presented in the table below:

	Low	High
Systolic blood pressure (mmHg)	≤ 90 mmHg or decrease from Baseline of ≥ 20 mmHg	≥ 180 mmHg, or increase from Baseline of ≥ 20 mmHg
Diastolic blood pressure (mmHg)	≤ 50 mmHg or decrease from Baseline of ≥ 20 mmHg	≥ 105 mmHg, or increase from Baseline of ≥ 20 mmHg
Pulse rate (bpm)	≤ 50 bpm or decrease from Baseline of ≥ 20 bpm	≥ 110 bpm or increase from Baseline of ≥ 20 bpm

Document: Z:\RPL554\AZA40375\Biostatistics\Documentation\SAP\Verona RPL554-DP-201 SAP v1.0 – Part A

Author: [name]

Version Number: 1.0

Version Date: [19DEC2018]

Template No.: CS_TP_BS016 Revision 5

Reference: CS_WI_BS005

Effective Date: 01Apr2018

Copyright © 2009, 2010, 2012, 2016, 2018 IQVIA. All rights reserved. The contents of this document are confidential and proprietary to IQVIA Holdings Inc. and its subsidiaries. Unauthorized use, disclosure or reproduction is strictly prohibited.

Peak supine pulse rate after single dose is defined as the maximum value measured in the first 4 hours post-dose. Peak pulse rate and change from baseline to peak will be summarized similarly to [Section 15.2.1.3](#), including the figure presentations. In addition, hypothesis testing as per Section [15.2.3](#), will be repeated for these endpoints.

16.5. PHYSICAL EXAMINATION

The following summaries will be provided for the full physical examination data, covering major body systems (nose, throat, skin, thyroid gland, neurological system, respiratory system, cardiovascular system, abdomen [liver and spleen], lymph nodes and extremities):

- Incidence of abnormalities at screening

The following summaries will be provided for a brief physical examination to be also performed, on skin, respiratory system, cardiovascular system, and abdomen (liver and spleen):

- Incidence of abnormalities pre-dose.

16.6. OTHER SAFETY ASSESSMENTS

Chest X-ray and inhalation training results will be presented in a listing only. In addition, screening serum and urine pregnancy test results, as well as pregnancy report data (current pregnancy, pregnancy history and details of the mother), will be listed for women of childbearing potential at Screening.

17. PHARMACOKINETIC EVALUATIONS

The primary endpoints of the study are the PK parameters AUC_{0-12h} and AUC_{0-t} , maximum concentration (C_{max}), time to maximum concentration (t_{max}) and half-life. PK concentrations are measured at the time of the single dosing and are collected on the Pharmacokinetic Samples eCRF page. Based on this information the PK parameters are then

Document: Z:\RPL554\AZA40375\Biostatistics\Documentation\SAP\Verona RPL554-DP-201 SAP v1.0 – Part A

Author: [name]

Version Number: 1.0

Version Date: [19DEC2018]

Template No.: CS_TP_BS016 Revision 5

Reference: CS_WI_BS005

Effective Date: 01Apr2018

Copyright © 2009, 2010, 2012, 2016, 2018 IQVIA. All rights reserved. The contents of this document are confidential and proprietary to IQVIA Holdings Inc. and its subsidiaries. Unauthorized use, disclosure or reproduction is strictly prohibited.

derived.

AUC_{0-t} represents the area under the plasma concentration curve from time 0 to last observed value above the lower limit of quantification and AUC_{0-12h} represents the area under the plasma concentration curve from time 0 to 12 hours. C_{max} denotes the highest plasma concentration measured and t_{max} denotes the timepoint corresponding to C_{max} . Half-life is the time required for the concentration to reduce to half its initial value, estimated as $\ln(2)/\lambda_z$.

Descriptive statistics (see [Appendix 1](#) [Programming conventions for outputs]) for the AUC parameters, C_{max} , t_{max} and half-life will be presented for all patients assigned to the PK analysis set for each treatment group.

Dose-normalization, the process of dividing the parameters by the administered dose, will be performed for each PK dose-dependent parameter (AUC_{0-t} , AUC_{0-12h} , C_{max}). No imputations for missing data will be applied.

The Power Model: $\log(Y_k) = \beta \times \log(D_k) + \epsilon_k$ where D is the total number of doses, N are the total number of doses $k=1,..,D$. Y_k is the measured response variable, $AUCs$ or C_{max} on the k th dose. ϵ_k is the error will be applied to assess dose proportionality. Dose proportionality requires β to be close to unity for dose dependent parameters. The estimate of β together with appropriate confidence interval (β_L, β_U) can be used to quantify the degree of non-proportionality. Analysis will be implemented using the SAS® procedure MIXED as follows:

```
PROC MIXED DATA = ...;
  CLASS PATIENT;
  MODEL PARAMETER = TREATMENT;
  ESTIMATE 'LOGTREATMENT - 1 unit' TREATMENT 1/CL ALPHA=0.1;
  ODS OUTPUT ESTIMATES = ESTIMATE;
  ODS OUTPUT SOLUTIONR = SOLUTION;
RUN;
```

where PATIENT = patient ID

PARAMETER = separate models for each of the log(parameters): log(AUC_{0-12h}) log(AUC_{0-t}) and log(C_{max})

TREATMENT = log (treatment group [RPL554 treatment groups])

Document: Z:\RPL554\AZA40375\Biostatistics\Documentation\SAP\Verona RPL554-DP-201 SAP v1.0 – Part A

Author: [name]

Version Number: 1.0

Version Date: [19DEC2018]

Template No.: CS_TP_BS016 Revision 5

Reference: CS_WI_BS005

Effective Date: 01Apr2018

Copyright © 2009, 2010, 2012, 2016, 2018 IQVIA. All rights reserved. The contents of this document are confidential and proprietary to IQVIA Holdings Inc. and its subsidiaries. Unauthorized use, disclosure or reproduction is strictly prohibited.

Summary statistics (For AUC and C_{max} parameters: n, geometric mean, coefficient of variation [CV], minimum, maximum and median and for t_{max} parameter: n, arithmetic mean, standard deviation, minimum, maximum and median) will also be presented.

Document: Z:\RPL554\AZA40375\Biostatistics\Documentation\SAP\Verona RPL554-DP-201 SAP v1.0 – Part A

Author: [name]

Version Number: 1.0

Version Date: [19DEC2018]

Template No.: CS_TP_BS016 Revision 5

Reference: CS_WI_BS005

Effective Date: 01Apr2018

Copyright © 2009, 2010, 2012, 2016, 2018 IQVIA. All rights reserved. The contents of this document are confidential and proprietary to IQVIA Holdings Inc. and its subsidiaries. Unauthorized use, disclosure or reproduction is strictly prohibited.

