9.4.6 Pharmacokinetics

The following PK parameters will be calculated from plasma concentrations of RPL554 using standard non-compartmental methods.

- Part A: AUC_{0-t} represents the area under the plasma concentration curve from time 0 to last observed value above the lower limit of quantification
- Part A: Half-life=ln(2)/λ_z
- Parts A and B: AUC_{0-12h} represents the area under the plasma concentration curve from time 0 to 12 hours. The AUC_{0-12h} value after dose 13 in Part B is considered an appropriate

estimate of the AUC at steady state. C_{max} denotes the highest plasma concentration measured

- t_{max} denotes the time point corresponding to C_{max}

PK parameters will be summarized by dose level using descriptive statistics (n, geometric mean, coefficient of variation [CV], minimum, maximum and median for AUC parameters, C_{max} , n, arithmetic mean, standard deviation, minimum, maximum and median for t_{max}).

In Part A, dose-normalized parameters (AUC_{0-t} and AUC_{0-12h}, C_{max}) will be compared using analysis of variance models with fixed factor treatment. In Part B, dose-normalized AUC_{0-12h} and C_{max} will be compared using analysis of covariance models adjusting for factors treatment, period and patient 90% confidence intervals will be constructed for the geometric mean ratios. If appropriate, AUC_{0-12h} data from Parts A and B belonging to the same patient and the same dose of RPL554 may be combined to compute the accumulation index (repeat dose/single dose ratio).

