3.3. CHANGES TO ANALYSIS FROM PROTOCOL

Not applicable.

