4.3. PART A ANALYSIS

All Part A analyses identified in this SAP will be performed by IQVIA Biostatistics following Database Lock on a clean database:

- All outstanding data issues and queries resolved.
- All irresolvable data issues documented in the Data Handling Report (DHR) from Data Management.
- All coding of medications and adverse events (AEs) completed.
- Serious AE (SAE) reconciliation completed.
- All reconciliation of vendor data with electronic case report form (eCRF) data completed successfully.
- Analysis sets authorized.

It should be noted that the main teams performing the Part A analysis will remain blinded at the time of the Part A database lock. This is to avoid any potential risk they could trace what study medication a patient might be receiving in Part B (e.g. if they know they experienced certain AEs while on one treatment in Part A and identify this in Part B).

All verbatim text from the eCRF will be presented in outputs “as is” with no “manual hard coding” corrections for such data. Also, PK analysis will be performed by another party (third party vendor), however details of this analysis will be specified in this SAP.

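### Part A SAP section 17 drops the protocol's ANOVA on dose-normalised PK without declaring it, and prints a power-model equation that contradicts its own code

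*SAP*

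**What the plan says.** **Protocol 9.4.6 (Pharmacokinetics).** For Part A, the dose-normalised AUC0-t, AUC0-12h and Cmax "will be compared using analysis of variance models with fixed factor treatment". The Part B model comes next, and a statement about 90% confidence intervals for geometric mean ratios follows directly after it. That statement plausibly covers both parts, but it is not tied to Part A explicitly. A power model is not mentioned.

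**Part A SAP, section 17.** The same three parameters are to be divided by the administered dose. No model, test or interval is then specified for the normalised values. Dose proportionality is assessed with a power model printed as "\log(Y_k) = \beta \times \log(D_k) + \epsilon_k", "where D is the total number of doses, N are the total number of doses". The criterion is: "Dose proportionality requires β to be close to unity for dose dependent parameters". No numerical limits are given.

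The SAS code that follows has "CLASS PATIENT" and "MODEL PARAMETER = TREATMENT", with no option to suppress the intercept. TREATMENT is defined as the log of the RPL554 dose group, and the slope gets a 90% confidence interval.

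**Part A SAP, section 3.3 (Changes to Analysis from Protocol).** The whole entry is "Not applicable".

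**Part A SAP, section 4.3.** "PK analysis will be performed by another party (third party vendor), however details of this analysis will be specified in this SAP".

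**The concern.** The PK profile is the Part A primary objective, and AUC0-12h, AUC0-t and Cmax are among its primary endpoints. The protocol names one between-dose comparison of these quantities. The SAP prepares the data for that comparison, omits it, and states that nothing has changed. A reader of the study report who relies on section 3.3 would not know that the protocol's analysis is missing or that the power model was added.

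The two analyses are not interchangeable. The power model summarises the whole dose range in one slope and assumes a straight line on the log-log scale. The ANOVA lets each dose have its own normalised mean, so it can show a pattern that is not a straight line.

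The equation is a second, smaller matter. A slope of 1 indicates proportionality only when the model has an intercept. An outside vendor works from this SAP, and the SAP gives it an equation and code that describe different models.

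**Working it through.** The documents give no power or precision figure for this analysis, so there is none to reproduce. The stated 40-fold range is consistent: 6000/150 = 40.

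**1. Protocol against SAP**

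| Item | Protocol 9.4.6, Part A | Part A SAP, section 17 |
|---|---|---|
| Dose-normalised AUC0-t, AUC0-12h, Cmax | Yes | Computed |
| ANOVA, fixed factor treatment | Yes | Absent |
| 90% CI for geometric mean ratios | Plausibly | Absent |
| Power model, 90% CI for slope | Not mentioned | Present |
| Change declared in 3.3 | n/a | None |

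The Part A SAP cites protocol version 1.0, and the protocol supplied is a later amendment. Its amendment list shows no change to 9.4.6, so the ANOVA was presumably already in version 1.0.

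**2. Equation against code**

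Inputs from the documents: doses 150, 500, 1500, 3000 and 6000 µg, with about 6 patients each. Assumption: exactly proportional PK, Y = c × dose in µg, with c from 0.001 to 10. The documents do not give c.

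Read literally, D is a count and the same for everyone, so no dose slope could be estimated. Reading D as the dose, let x = ln(dose).

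- No intercept, as printed: slope = Σxy/Σx² = 1 + ln(c) × Σx/Σx².
- Dose in µg: Σx = 35.244 and Σx² = 256.994 over the five doses, so Σx/Σx² = 0.1371.
- Dose in mg: the same ratio is 0.0815, and the slope is 1 + 0.0815 × ln(1000c).
- With intercept, as coded: slope = Sxy/Sxx, in which c and the dose unit cancel.

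| c | Printed, µg | Printed, mg | Coded |
|---|---|---|---|
| 0.001 | 0.053 | 1.000 | 1.000 |
| 0.01 | 0.368 | 1.188 | 1.000 |
| 0.1 | 0.684 | 1.375 | 1.000 |
| 1 | 1.000 | 1.563 | 1.000 |
| 10 | 1.316 | 1.750 | 1.000 |

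The printed form can also hide non-proportionality. A true exponent of 0.7 with c = 10 gives 0.7 + 0.1371 × ln(10) = 1.016, where the coded model returns 0.700.

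In 3,000 simulated trials per setting (30 active patients, dose in µg, assumed between-patient CV 30%, 50% and 80%), the 90% CI from the coded model wrongly excluded 1 in about 9% to 12% of trials, against a nominal 10%. The CI from the printed model excluded 1 in every trial unless c = 1.

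**3. Precision of each analysis**

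Assumed CVs as above, with s = √ln(1 + CV²) = 0.294, 0.472 and 0.703.

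- Slope: 90% half-width = t(0.95; 28) × s/√Sxx, with t = 1.701 and Sxx = 51.37 for 30 patients. This gives ±0.07, ±0.11 and ±0.17.
- Ratio of two doses from the ANOVA: the 90% CI multiplies and divides the ratio by exp[t(0.95; 25) × s × √(1/6 + 1/6)], with t = 1.708. This gives factors of about 1.34, 1.59 and 2.0.

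**The case against.** The strongest reply is that the SAP states it will implement the analysis with the PROC MIXED code, and that code is sound. It has an intercept, uses log dose as a continuous regressor and gives a slope that does not depend on units. This stands. A reader might infer from the equation that the planned proportionality assessment is invalid, but the documents do not support that. The unit-dependent slopes in the working describe only what would happen if someone fitted the equation and set the code aside. The garbled definition of D makes that less likely, since a count cannot serve as the regressor.

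A reader might also infer that the choice of Part B doses was put at risk. The protocol's amendment summary does not support that either: all four lower doses went forward, and 6000 µg was excluded by the original protocol. No eligible dose was dropped.

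Three further points limit the ANOVA omission.

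- Dose proportionality is not itself a listed Part A objective or endpoint, and descriptive PK statistics by treatment group remain planned.
- The dose-normalisation step is kept. Only the comparison is missing.
- With about 6 patients per arm, the dose-to-dose ratios are too imprecise to identify the exact dose at which exposure departs from proportionality.

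All three are fair. None explains why an analysis written into the protocol is absent while section 3.3 reports no change. Protocol 9.1 already requires deviations to be justified in the study report, but section 3.3 as it stands would not prompt anyone to do so.

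**Conclusion.** The point holds in two parts of unequal weight.

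The main part is an undeclared departure. The protocol's comparison of three dose-normalised parameters is missing from the SAP, a power model that 9.4.6 does not mention is used, and section 3.3 says no change applies. This rests on the text alone, apart from two caveats: protocol version 1.0 was not available, and the 90% CI sentence reaches Part A only by a plausible reading.

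The smaller part is a text error. The equation lacks an intercept and misdefines D, in conflict with valid code. Its effect on the planned result is nil if the code is run. If the equation is followed, the slope under exact proportionality would range from 0.05 to 1.32 with dose in µg, for assumed c between 0.001 and 10.

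This should be corrected. It does not make the planned slope invalid. The restored ratios would supplement that slope, with 90% limits of roughly a factor of 1.3 to 2.0 either way under the assumed CVs.

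**What to change.** - **Section 17, comparison:** add an ANOVA with treatment as fixed factor on log dose-normalised AUC0-t, AUC0-12h and Cmax, reporting geometric mean ratios between doses with 90% CIs.
- **Section 17, equation:** write log(Y_k) = α + β × log(Dose_k) + ε_k, where Dose_k is the administered dose in µg for patient k. This matches the code. Keep the 90% CI for β.
- **Section 3.3:** list the power model as an addition to the protocol.
- **Clinical study report:** the protocol amendment says Part A is complete and selected data analysed, so this is a change made after analysis. Report the restored comparison and the deviation there, as protocol 9.1 requires, and confirm with the vendor that the fitted model had an intercept and used log dose. Present the ratios as a supplement to the slope.

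The cost is some SAP wording and one small table per parameter. No new data are needed, because the normalised values are already planned.

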APPENDIX 1. PROGRAMMING CONVENTIONS FOR OUTPUTS

IQVIA OUTPUT CONVENTIONS

Outputs will be presented according to the following:

TABLE AND LISTING OUTPUT CONVENTIONS

General:

- The first row in the body of the table or listing should be blank
- The left-hand column should start in column 1. No indenting or centering of the output should occur.
- Rounding should be done with the SAS function ROUND.
- Numbers in tables should be rounded, not truncated.
- Alphanumeric output should be left aligned.
- Numbers should be decimal point aligned.
- Whole numbers should be right aligned.
- Text values should be left aligned.
- The first letter of a text entry should be capitalized
- Listings of adverse events, concomitant medications, medical histories etc. should be sorted in chronological order, with earliest adverse event, medication or history coming first.
- The study drug should appear first in tables with treatments as columns
- In general, only present totals (across treatment groups) at baseline/randomization, and do not present them post randomization, unless the customer specifically requests it.
- All listing outputs should be sorted (preferably by Treatment, Site Number and Patient Number).
- Exponentiation will be expressed using a superscript with ODS RTF.
- All variables that are output in the CRF (which have data present) should appear in the listings, along with all derived data appearing in the corresponding tables

Document: Z:\RPL554\AZA40375\Biostatistics\Documentation\SAP\Verona RPL554-DP-201 SAP v1.0 – Part A

Author: [name]

Version Number: 1.0

Version Date: [19DEC2018]

Template No.: CS_TP_BS016 Revision 5

Reference: CS_WI_BS005

Effective Date: 01Apr2018

Copyright © 2009, 2010, 2012, 2016, 2018 IQVIA. All rights reserved. The contents of this document are confidential and proprietary to IQVIA Holdings Inc. and its subsidiaries. Unauthorized use, disclosure or reproduction is strictly prohibited.

- The width of the entire output should match the linesize.

Univariate Statistics:

- Statistics should be presented in the same order across tables (i.e., n, Mean, SD, Minimum, Median, Maximum and equivalently, n, GeoMean, CV, Minimum, Median, Maximum)
- Table statistics should line up under the N part of the (N=XXX) in the table header. All decimal points should line up. If the minimum and maximum are output on 1 line as Minimum, Maximum then the comma should line up with the decimal point.
- If the original data has N decimal places, then the summary statistics should have the following decimal places:
Minimum and maximum: N
Mean, median and CV%: N + 1
SD: N + 2

Frequencies and percentages (n and %):

- Percent values should be reported inside parentheses, with 1 space between the count and the left parenthesis of the percentage. Parentheses should be justified to accept a maximum of 100.0 as a value and padded with blank space if the percent is less than 100.0. An example is given below:

77 (100.0%)

50 (64.9%)

0 (0.0%)

- Percentages will be reported to 1 decimal place, except percentages <100.0% but >99.9% will be presented as '>99.9%' (e.g., 99.99% is presented as >99.9%); and percentages < 0.1% will be presented as '<0.1%' (e.g., 0.08% is presented as <0.1%). Rounding will be applied after the <0.1% and >99.9% rule.

e.g. (<0.1%)

(6.8%)

(>99.9%)

Percentages may be reported to 0 decimal places as appropriate (for example, where the denominator is relatively

Document: Z:\RPL554\AZA40375\Biostatistics\Documentation\SAP\Verona RPL554-DP-201 SAP v1.0 – Part A

Author: [name]

Version Number: 1.0

Version Date: [19DEC2018]

Template No.: CS_TP_BS016 Revision 5

Reference: CS_WI_BS005

Effective Date: 01Apr2018

Copyright © 2009, 2010, 2012, 2016, 2018 IQVIA. All rights reserved. The contents of this document are confidential and proprietary to IQVIA Holdings Inc. and its subsidiaries. Unauthorized use, disclosure or reproduction is strictly prohibited.

small).

- Where counts are zero, percentages of 0.0% should appear in the output.

Confidence Intervals:

- As a rule, confidence intervals are output to 1 place more than the raw data, and standard deviations and standard errors to 2 places more than the raw data
- Confidence intervals should be justified so that parentheses displayed on consecutive lines of a table “line up”.
- Boundary values of confidence intervals should be separated by a comma.
- Boundary values should be padded as necessary to accept negative values and to allow alignment of the decimal place.
- An example is given below:
(-0.12, -0.10)
(9.54, 12.91)

P-values:

- P-values should be reported to 3 decimal places, except values <1.000 but >0.999 will be presented as ‘>0.999’ (e.g., 0.9998 is presented as >0.999); and values <0.001 will be presented as ‘<0.001’ (e.g., 0.0009 is presented as <0.001). Rounding will be applied after the <0.001 and >0.999 rule

Ratios:

- Ratios should be reported to 1 more decimal place than the original data.

Spacing:

- There must be a minimum of 1 blank space between columns (preferably 2)

Denominators:

- If a different count other than the population count is used for a denominator (within the table) to calculate percentages, there should be a row in the table that identifies that number “n”.

Document: Z:\RPL554\AZA40375\Biostatistics\Documentation\SAP\Verona RPL554-DP-201 SAP v1.0 – Part A

Author: [name]

Version Number: 1.0

Version Date: [19DEC2018]

Template No.: CS_TP_BS016 Revision 5

Reference: CS_WI_BS005

Effective Date: 01Apr2018

Copyright © 2009, 2010, 2012, 2016, 2018 IQVIA. All rights reserved. The contents of this document are confidential and proprietary to IQVIA Holdings Inc. and its subsidiaries. Unauthorized use, disclosure or reproduction is strictly prohibited.

- Alternatively, a footnote should be included in each table with percentages to indicate the denominator for percentages.

Missing values

- A “0” should be used to indicate a zero frequency.
- A blank will be used to indicate missing data in an end-of-text table or patient listing.

FIGURE OUTPUT CONVENTIONS

- Figures should be provided in RTF files generated by SAS.
- Should contain the title or footer.
- The image should be clear and of high quality when viewed in the Word document, and when printed.
- In general, boxes around the figures should be used.

DATES & TIMES

Depending on data available, dates and times will take the form DDMMYY YYYY THH:MM:SS.

SPELLING FORMAT

English US.

PRESENTATION OF TREATMENT GROUPS

For outputs, treatment groups will be represented as follows and in this order:

Treatment Group	For Tables, Graphs and Listings
RPL554 150 µg double blind	RPL554 150µg
RPL554 500 µg double blind	RPL554 500µg

Document: Z:\RPL554\AZA40375\Biostatistics\Documentation\SAP\Verona RPL554-DP-201 SAP v1.0 – Part A

Author: [name]

Version Number: 1.0

Version Date: [19DEC2018]

Template No.: CS_TP_BS016 Revision 5

Reference: CS_WI_BS005

Effective Date: 01Apr2018

Copyright © 2009, 2010, 2012, 2016, 2018 IQVIA. All rights reserved. The contents of this document are confidential and proprietary to IQVIA Holdings Inc. and its subsidiaries. Unauthorized use, disclosure or reproduction is strictly prohibited.

Treatment Group	For Tables, Graphs and Listings
RPL554 1500 µg double blind	RPL554 1500µg
RPL554 3000 µg double blind	RPL554 3000µg
RPL554 6000 µg double blind	RPL554 6000µg
Placebo	Placebo
Non-randomized (where applicable)	Non-randomized

PRESENTATION OF VISITS

For outputs, visits will be represented as follows and in that order:

Long Name (default)	Short Name
Screening	Scr
Day 1	Day 1
Day 2	Day 2

LISTINGS

All listings will be ordered by the following (unless otherwise indicated in the template):

Randomized treatment group (or treatment received if it's a safety output), first by active dose [by ascending dose group] and then placebo.

Center-patient ID,

Date (where applicable),

For listings where non-randomized patients are included, these will appear in a category after the randomized treatment groups labeled 'Non-randomized'.

Document: Z:\RPL554\AZA40375\Biostatistics\Documentation\SAP\Verona RPL554-DP-201 SAP v1.0 – Part A

Author: [name]

Version Number: 1.0

Version Date: [19DEC2018]

Template No.: CS_TP_BS016 Revision 5

Reference: CS_WI_BS005

Effective Date: 01Apr2018

Copyright © 2009, 2010, 2012, 2016, 2018 IQVIA. All rights reserved. The contents of this document are confidential and proprietary to IQVIA Holdings Inc. and its subsidiaries. Unauthorized use, disclosure or reproduction is strictly prohibited.

